			SD	X.XXX	X.XXX	X.XXX			
			Minimum	X.XX	X.XX	X.XX			
			Median	X.X	X.X	X.X			
			Maximum	XX.X	XX.X	XX.X			
		Baseline*	n	XX	XX	XX			
			Mean	X.XX	X.XX	X.XX			
			SD	X.XXX	X.XXX	X.XXX			
			Minimum	X.XX	X.XX	X.XX			
			Median	X.X	X.X	X.X			
			Maximum	XX.X	XX.X	XX.X			
		Day X, Hour X.XX	n	XX	XX	XX	XX	XX	XX
			Mean	X.XX	X.XX	X.XX	X.XX	X.XX	X.XX
			SD	X.XXX	X.XXX	X.XXX	X.XXX	X.XXX	X.XXX
			Minimum	X.XX	X.XX	X.XX	X.XX	X.XX	X.XX
			Median	X.X	X.X	X.X	X.X	X.X	X.X
			Maximum	XX.X	XX.X	XX.X	XX.X	XX.X	XX.X

<include all timepoints>

Note: # = Lowest of the lower ranges and highest of the higher ranges are used. Refer to Appendix 16.1.10.1 for the breakdown.

* Baseline is defined as the result closest and prior to dose on Day 1.

Program: /AAXXXX/ECR/sas_prg/stsas/tab_PROGRAMNAME.sas DDMMYYYY HH:MM

Tables 14.3.5.2 and 14.3.5.4 will be in the following format:

Page 1 of X

Table 14.3.5.2 Clinical Laboratory Shift From Baseline - Serum Chemistry (Safety Population)

Laboratory Test (unit)	Treatment	Time Point	Baseline* L			Baseline* N			Baseline* H		
			L	N	H	L	N	H	L	N	H
XXXXXX (unit)	XXX <units>	Day X, Hour X.XX	X	XX	X	X	XX	X	X	XX	X

Note: 1.5 µg/kg: 0.5 µg/kg bolus dose of E-WE Thrombin followed by a 0.25 µg/kg/hour continuous infusion over 4 hours for a total dose of 1.5 µg/kg

3.0 µg/kg: 1.0 µg/kg bolus dose of E-WE Thrombin followed by a 0.5 µg/kg/hour continuous infusion over 4 hours for a total dose of 3.0 µg/kg

Placebo = pooled placebo

N = Within Normal Range, L = Below Normal Range, H = Above Normal Range

* Baseline is defined as the result closest and prior to dose on Day 1.

Program: /AXXXXX/ECR/sas_prg/stsas/tab_PROGRAMNAME.sas DDMMYYYY HH:MM

Table 14.3.5.5 Clinical Laboratory Summary - Coagulation and Platelet Count (Safety Population)

Laboratory Test (unit)	Reference Range	Time Point	Statistic	1.5 µg/kg E-WE Thrombin			3.0 µg/kg E-WE Thrombin			Placebo (Pooled)		
				Pre-HD	Post-HD	Fold Change	Pre-HD	Post-HD	Fold Change	Pre-HD	Post-HD	Fold Change
XXXXXXXXXX (unit)	X.X-XX.X#	Screen	n	XX		XX		XX		XX		XX
			Mean	X.XX		X.XX		X.XX		X.XX		X.XX
			SD	X.XXX		X.XXX		X.XXX		X.XXX		X.XXX
			Minimum	X.XX		X.XX		X.XX		X.XX		X.XX
			Median	X.X		X.X		X.X		X.X		X.X
			Maximum	XX.X		XX.X		XX.X		XX.X		XX.X
		Day -8	n	XX		XX		XX		XX		XX
			Mean	X.XX		X.XX		X.XX		X.XX		X.XX
			SD	X.XXX		X.XXX		X.XXX		X.XXX		X.XXX
			Minimum	X.XX		X.XX		X.XX		X.XX		X.XX
			Median	X.X		X.X		X.X		X.X		X.X
			Maximum	XX.X		XX.X		XX.X		XX.X		XX.X
		Day X	n	XX	XX	XX	XX	XX	XX	XX	XX	XX
			Mean	X.XX	X.XX	X.XX	X.XX	X.XX	X.XX	X.XX	X.XX	X.XX
			SD	X.XXX	X.XXX	X.XXX	X.XXX	X.XXX	X.XXX	X.XXX	X.XXX	X.XXX
			Minimum	X.XX	X.XX	X.XX	X.XX	X.XX	X.XX	X.XX	X.XX	X.XX
			Median	X.X	X.X	X.X	X.X	X.X	X.X	X.X	X.X	X.X
			Maximum	XX.X	XX.X	XX.X	XX.X	XX.X	XX.X	XX.X	XX.X	XX.X

<include all remaining HD days>

Programmer note: This table will include aPTT, PT, INR, PT/INR, fibrinogen, TT from coagulation and platelet count from hematology. for PT, INR and PT/INR, the pre-dialysis value will be the baseline value for that day and the "change from baseline" will be the fold change from baseline "ie. Post-dialysis / Pre-dialysis.

Note: # = Lowest of the lower ranges and highest of the higher ranges are used. Refer to Appendix 16.1.10.1 for the breakdown.
 Fold change = Post-dialysis / Pre-dialysis

Program: /AAXXXX/ECR/sas_prg/stsas/tab_PROGRAMNAME.sas DDMMYYYY HH:MM

Table 14.3.5.6 Vital Sign Summary and Change from Baseline(Safety Population)

Vital Sign(unit)	Time Point	Statistic	Dose Level of E-WE Thrombin			Change from Baseline*		
			1.5 µg/kg	3.0 µg/kg	Placebo (Pooled)	1.5 µg/kg	3.0 µg/kg	Placebo (Pooled)
XXXXXXXXXX (unit)	Screen	n	XX	XX	XX			
		Mean	X.XX	X.XX	X.XX			
		SD	X.XXX	X.XXX	X.XXX			
		Minimum	X.XX	X.XX	X.XX			
		Median	X.X	X.X	X.X			
		Maximum	XX.X	XX.X	XX.X			
<Also include Days -8, -7, -5 and -2>								
Baseline*		n	XX	XX	XX			
		Mean	X.XX	X.XX	X.XX			
		SD	X.XXX	X.XXX	X.XXX			
		Minimum	X.XX	X.XX	X.XX			
		Median	X.X	X.X	X.X			
		Maximum	XX.X	XX.X	XX.X			
Day X, Hour X.XX		n	XX	XX	XX	XX	XX	XX
		Mean	X.XX	X.XX	X.XX	X.XX	X.XX	X.XX
		SD	X.XXX	X.XXX	X.XXX	X.XXX	X.XXX	X.XXX
		Minimum	X.XX	X.XX	X.XX	X.XX	X.XX	X.XX
		Median	X.X	X.X	X.X	X.X	X.X	X.X
		Maximum	XX.X	XX.X	XX.X	XX.X	XX.X	XX.X

Note: * Baseline is defined as the result closest and prior to the dose on Day 1.

Program: /AXXXXXX/ECR/sas_prg/stsas/tbl PROGRAMNAME.sas DDMMYYYY HH:MM

Table 14.3.5.7 Summarization of Weight (Safety Population)

Time Point	Statistic	Dose Level of E-WE Thrombin		
		1.5 µg/kg	3.0 µg/kg	Placebo (Pooled)
Screen	n	XX	XX	XX
	Mean	X.XX	X.XX	X.XX
	SD	X.XXX	X.XXX	X.XXX
	Minimum	X.XX	X.XX	X.XX
	Median	X.X	X.X	X.X
	Maximum	XX.X	XX.X	XX.X
Day -8, Check-in	n	XX	XX	XX
	Mean	X.XX	X.XX	X.XX
	SD	X.XXX	X.XXX	X.XXX
	Minimum	X.XX	X.XX	X.XX
	Median	X.X	X.X	X.X
	Maximum	XX.X	XX.X	XX.X
Day -7, Before HD	n	XX	XX	XX
	Mean	X.XX	X.XX	X.XX
	SD	X.XXX	X.XXX	X.XXX
	Minimum	X.XX	X.XX	X.XX
	Median	X.X	X.X	X.X
	Maximum	XX.X	XX.X	XX.X

<Also include before and after HD timepoints on Days -7, -5, -2, 1 and 3>

Program: /AAXXXX/ECR/sas_prg/stsas/tabc_PROGRAMNAME.sas DDMMYYYY HH:MM

Table 14.3.5.8 12-Lead Electrocardiogram Summary and Change from Baseline (Safety Population)

Measurement (unit)	Time Point	Statistic	Dose Level of E-WE Thrombin			Change from Baseline*		
			1.5 µg/kg	3.0 µg/kg	Placebo (Pooled)	1.5 µg/kg	3.0 µg/kg	Placebo (Pooled)
XXXXXXXXX (unit)	Screen	n	XX	XX	XX			
		Mean	X.XX	X.XX	X.XX			
		SD	X.XXX	X.XXX	X.XXX			
		Minimum	X.XX	X.XX	X.XX			
		Median	X.X	X.X	X.X			
		Maximum	XX.X	XX.X	XX.X			
	Day -8 Check-in*	n	XX	XX	XX			
		Mean	X.XX	X.XX	X.XX			
		SD	X.XXX	X.XXX	X.XXX			
		Minimum	X.XX	X.XX	X.XX			
		Median	X.X	X.X	X.X			
		Maximum	XX.X	XX.X	XX.X			
	Day 1, Hour X.XX	n	XX	XX	XX	XX	XX	XX
		Mean	X.XX	X.XX	X.XX	X.XX	X.XX	X.XX
		SD	X.XXX	X.XXX	X.XXX	X.XXX	X.XXX	X.XXX
		Minimum	X.XX	X.XX	X.XX	X.XX	X.XX	X.XX
		Median	X.X	X.X	X.X	X.X	X.X	X.X
		Maximum	XX.X	XX.X	XX.X	XX.X	XX.X	XX.X
	Day 3, Hour X.XX	n	XX	XX	XX	XX	XX	XX
		Mean	X.XX	X.XX	X.XX	X.XX	X.XX	X.XX
		SD	X.XXX	X.XXX	X.XXX	X.XXX	X.XXX	X.XXX
		Minimum	X.XX	X.XX	X.XX	X.XX	X.XX	X.XX
		Median	X.X	X.X	X.X	X.X	X.X	X.X
		Maximum	XX.X	XX.X	XX.X	XX.X	XX.X	XX.X

Note: * Baseline is Day -8 Check-in.

Program: /AXXXXXX/ECR/sas_prg/stsas/tab_PROGRAMNAME.sas DDMMMYYYY HH:MM

Table 14.3.5.9 Summarization of Bleeding Time (Safety Population)

Time Point	Statistic	Dose Level of E-WE Thrombin		
		1.5 µg/kg	3.0 µg/kg	Placebo (Pooled)
Day -7	n	XX	XX	XX
	Mean	X.XX	X.XX	X.XX
	SD	X.XXX	X.XXX	X.XXX
	Minimum	X.XX	X.XX	X.XX
	Median	X.X	X.X	X.X
	Maximum	XX.X	XX.X	XX.X
Day -5	n	XX	XX	XX
	Mean	X.XX	X.XX	X.XX
	SD	X.XXX	X.XXX	X.XXX
	Minimum	X.XX	X.XX	X.XX
	Median	X.X	X.X	X.X
	Maximum	XX.X	XX.X	XX.X
Day -2	n	XX	XX	XX
	Mean	X.XX	X.XX	X.XX
	SD	X.XXX	X.XXX	X.XXX
	Minimum	X.XX	X.XX	X.XX
	Median	X.X	X.X	X.X
	Maximum	XX.X	XX.X	XX.X

<Also include Days 1 and 3>

Programmer note: Bleeding time is recorded on the Dialyzer Assessment CRF page under item #4 as length of time of pressure on puncture site.

Note: Bleeding time in minutes was assessed immediately after the end of hemodialysis
and removal of the needles from the fistula or graft.

Program: /AXXXXXX/ECR/sas_prg/stsas/tab_PROGRAMNAME.sas DDMMYY HH:MM

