8.2.2.1 Safety Data

There were no deaths or serious AEs (SAEs) experienced in Study No. EWE-17-01 [Celerion Project No.: CA19169]. No subjects were discontinued due to AEs.

Overall, 4 of 21 (19%) subjects experienced a total of 8 treatment-emergent AEs (TEAEs) in this study, with 3 of 16 (19%) subjects following active treatment and 1 of 5 subjects (20%) following placebo. The majority of the events (5) were mild (Grade 1) in severity and 3 were moderate (Grade 2). Of the 8 TEAEs reported, only one was suspected to be possibly treatment related by the Principal Investigator (PI).

The most common TEAE was headache, experienced by 2 (13%) active-treatment subjects. One case of headache of moderate severity (Grade 2) was deemed to be possibly treatment related by the PI and had a reported onset of approximately 10 minutes after dosing, resolving 36 hours later. The other case of headache (Grade 1) was deemed to be unrelated to treatment by the PI and was reported 17 days after dosing, resolving 24 hours later. Other TEAEs reported included back pain, pruritus, papular rash and skin exfoliation in one placebo subject and vessel puncture site hemorrhage at the site of IV attempt in one active treatment subject.

Temporal aPTT prolongation was not evaluated as an AE, because it was an expected response, indicating a natural response to activation of endogenous protein C and release of some APC into systemic circulation.

A single IV dose of E-WE thrombin up to 4 µg/kg appeared to be safe and generally well tolerated by the healthy male and female subjects in this study.

[figure not shown]

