9.2 Study Endpoints

Primary outcome measures:

- The safety and tolerability of E-WE thrombin following active treatment will be evaluated versus pre-treatment and placebo by number and severity of AEs (including HD vascular access site reactions), physical examinations, bleeding time from the HD vascular access sites, vital sign measurements, 12-lead ECGs, clinical laboratory tests, and coagulation tests.

Secondary outcome measures:

- PD of E-WE thrombin will be measured by APC-PCI and plasma APC-PCI will act as a surrogate marker for E-WE thrombin drug exposure.
- Efficacy of antithrombotic activity will be evaluated by thrombus accumulation within the dialyzer cartridge (evaluated by visual inspection) after E-WE thrombin active treatment versus pre-treatment and placebo.
- Efficiency of HD will be assessed using BUN levels before and after dialysis to determine urea removed by 4 hours of dialysis (Kt/V and URR) after E-WE thrombin active treatment versus pre-treatment and placebo.

Other outcome measures:

- Development of antibodies to E-WE thrombin or WT thrombin after drug exposure.

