2.2 Endpoints

Primary outcome measures:

- The safety and tolerability of E-WE thrombin following administration of the active treatment will be evaluated versus pre-treatment and placebo by number and severity of AEs (including HD vascular access site reactions), physical examinations, bleeding time from the HD vascular access sites, vital sign measurements, 12-lead ECGs, clinical laboratory tests, and coagulation tests.

Secondary outcome measures:

- Pharmacodynamics of E-WE thrombin will be measured by APC-PCI and plasma APC-PCI will act as a surrogate marker for E-WE thrombin drug exposure.
- Efficacy of antithrombotic activity will be evaluated by thrombus accumulation within the dialyzer cartridge (evaluated by visual inspection) after E-WE thrombin active treatment versus pre-treatment and placebo.
- Efficiency of HD will be assessed using BUN levels before and after dialysis to determine urea removed by 4 hours of dialysis (Kt/V and URR) after E-WE thrombin active treatment versus pre-treatment and placebo.

Other outcome measures:

- Development of antibodies to E-WE thrombin or WT thrombin after drug exposure.

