7.3 Adverse Events

All adverse events (AEs) occurring during this clinical trial will be coded using the Medical Dictionary for Regulatory Activities (MedDRA®), Version 21.1.

All AEs captured in the database will be listed in by-subject data listings including verbatim term, coded term, treatment, severity, relationship to study medication, and action; however, only treatment-emergent AEs (TEAEs) will be summarized.

A TEAE is defined as an AE that is starting or worsening at the time of or after study drug administration. Each TEAE will be attributed to a treatment based on the onset date and time of the AE. If the onset time of an AE is missing and the onset date is the same as the treatment dosing date, then the AE will be considered treatment emergent. If the onset date of an AE is missing, then the AE will be considered treatment emergent.

TEAEs will be tabulated by System Organ Class (SOC) and Preferred Term. Summary tables will include number of subjects reporting the AE and as percent of number of subjects dosed by treatment and overall. The number of AEs will be tabulated in a similar manner. Tables which tabulate the number of TEAEs by severity and relationship to study treatment will also be included.

Serious adverse events (SAEs), if present, will also be listed. Applicable narratives will be included in the CSR.

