14.3 Safety Data Summary Tables

14.3.1 Displays of Adverse Events

Table 14.3.1.1 Treatment-emergent Adverse Event Frequency by Treatment – Number of Subjects Reporting the Event (% of Subject Dosed) (Safety Population)

Table 14.3.1.2 Treatment-emergent Adverse Event Frequency by Treatment – Number of Adverse Events (% of Total Adverse Events) (Safety Population)

Table 14.3.1.3 Treatment-emergent Adverse Event Frequency by Treatment, Severity, and Relationship to Drug – Number of Adverse Events (Safety Population)

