 If a subject has 2 or more clinical adverse events, the subject is counted only once within a category. The same subject may appear in different categories.

Program: /CAXXXX/sas_prg/stsas/tab_PROGRAMNAME.sas DDMMYYYY HH:MM

Table 14.3.1.2 Treatment-Emergent Adverse Event Frequency by Treatment – Number of Adverse Events
 (% of Total Adverse Events) (Safety Population)

Adverse Event*	Dose Level of E-WE Thrombin			
	1.5 µg/kg	3.0 µg/kg	Placebo (Pooled)	Overall
Number of TEAEs	X (100%)	X (100%)	X (XX%)	X (XX%)
Nervous system disorders	X (XX%)	X (XX%)	X (XX%)	X (XX%)
Dizziness	X (XX%)	X (XX%)	X (XX%)	X (XX%)
Headache	X (XX%)	X (XX%)	X (XX%)	X (XX%)
Presyncope	X (XX%)	X (XX%)	X (XX%)	X (XX%)
Respiratory, thoracic and mediastinal disorders	X (XX%)	X (XX%)	X (XX%)	X (XX%)
Dry throat	X (XX%)	X (XX%)	X (XX%)	X (XX%)
Oropharyngeal pain	X (XX%)	X (XX%)	X (XX%)	X (XX%)
Sinus congestion	X (XX%)	X (XX%)	X (XX%)	X (XX%)
Sneezing	X (XX%)	X (XX%)	X (XX%)	X (XX%)
General disorders and administration site conditions	X (XX%)	X (XX%)	X (XX%)	X (XX%)
Fatigue	X (XX%)	X (XX%)	X (XX%)	X (XX%)
Thirst	X (XX%)	X (XX%)	X (XX%)	X (XX%)

Note: *Adverse events are classified according to MedDRA Version 21.1. ^ = Treatment-emergent adverse events

Program: /CAXXXX/sas_prg/stsas/tab_PROGRAMNAME.sas DDMMMYYYY HH:MM

Table 14.3.1.3 Treatment-Emergent Adverse Event Frequency by Treatment, Severity, and Relationship to Study Drug – Number of Adverse Events (Safety Population)

Adverse Event*	Cohort/ Treatment	Number of Subjects With TEAEs	Number of TEAEs	Severity				Relationship to Study Drug			
				Grade 1	Grade 2	Grade 3	Grade 4	Unrelated	Unlikely	Possibly	Probably
Dizziness	1/A	X	X	X	X	X	X	X	X	X	X
	X/X	X	X	X	X	X	X	X	X	X	X
Dry eye	X/X	X	X	X	X	X	X	X	X	X	X
Dry mouth	X/X	X	X	X	X	X	X	X	X	X	X
Dry throat	X/X	X	X	X	X	X	X	X	X	X	X
Ear pain	X/X	X	X	X	X	X	X	X	X	X	X
Fatigue	X/X	X	X	X	X	X	X	X	X	X	X
Headache	X/X	X	X	X	X	X	X	X	X	X	X
Dizziness	X/X	X	X	X	X	X	X	X	X	X	X
Hyperhidrosis	X/X	X	X	X	X	X	X	X	X	X	X
Laceration	X/X	X	X	X	X	X	X	X	X	X	X
Limb crushing injury	X/X	X	X	X	X	X	X	X	X	X	X
Muscle twitching	X/X	X	X	X	X	X	X	X	X	X	X
1.5 µg/kg E-WE Thrombin	X	X	X	X	X	X	X	X	X	X	X
3.0 µg/kg E-WE Thrombin	X	X	X	X	X	X	X	X	X	X	X
Placebo (Pooled)	X	X	X	X	X	X	X	X	X	X	X
Overall	XX	XX	X	X	X	X	X	X	X	X	X

Note: Treatment: A = 0.5 µg/kg bolus dose of E-WE Thrombin followed by a 0.25 µg/kg/hour continuous infusion over 4 hours for a total dose of 1.5 µg/kg

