B = 1.0 µg/kg bolus dose of E-WE Thrombin followed by a 0.5 µg/kg/hour continuous infusion over 4 hours for a total dose of 3.0 µg/kg

P = Placebo

*Adverse events are classified according to MedDRA Version 21.1. TEAE = Treatment-emergent adverse events

If a subject experience the same adverse event (AE) at more than one level of severity during a treatment, each AE is counted separately. If a subject experience the same AE at more than one level of drug relationship during a treatment, each AE is counted separately.

Severity: Grade 1 = Mild; Grade 2 = Moderate; Grade 3 = Severe; Grade 4 = Potentially life-threatening

Program: /CAXXXX/sas_prg/stsas/tab_PROGRAMNAME.sas DDMMYYYY HH:MM

Aronora, Inc.
 E-WE thrombin, Protocol EWE-19-02
 Celerion, Clinical Study Report No. CA26622

Tables 14.3.4.1 to 14.3.4.3 will have the following format:

Page 1 of X

Table 14.3.4.1 Out-of-Range Values and Clinically Significant Results - Serum Chemistry (Safety Population)

Subject Number	Cohort/ Treatment	Age#/ Sex	Study Visit	Hour	Date	Time	Parameter1	Parameter2	Parameter3	Parameter4	Parameter5
							<Range> (Unit)	<Range> (Unit)	<Range> (Unit)	<Range> (Unit)	<Range> (Unit)
X	1/A	XX/X	Screen	.	DDMMYYYY	HH:MM:SS	XX H +				XX L
			Day X	XX	DDMMYYYY	HH:MM:SS	XX L	XX L	XX H	XX L	
			Unscheduled		DDMMYYYY	HH:MM:SS				XX	

Programmer Notes: Replace Parameter1, 2 etc. with actual lab tests in the study. Sort unscheduled assessment and early termination chronologically with other scheduled assessments.

Note: Treatment: A = 0.5 µg/kg bolus dose of E-WE Thrombin followed by a 0.25 µg/kg/hour continuous infusion over 4 hours for a total dose of 1.5 µg/kg

B = 1.0 µg/kg bolus dose of E-WE Thrombin followed by a 0.5 µg/kg/hour continuous infusion over 4 hours for a total dose of 3.0 µg/kg

P = Placebo

#Age is calculated at the time of first dosing. F = Female; M = Male

H = Above reference range, L = Below reference range

PI Interpretation: + = Clinically significant

Program: /CAXXXX/sas_prg/stsas/tab_PROGRAMNAME.sas DDMMYYYY HH:MM

Tables 14.3.5.1 and 14.3.5.3 will be in the following format:

Page 1 of X

Table 14.3.5.1 Clinical Laboratory Summary and Change from Baseline - Serum Chemistry (Safety Population)

Laboratory Test (unit)	Reference Range	Time Point	Statistic	Dose Level of E-WE Thrombin			Change from Baseline*		
				1.5 µg/kg	3.0 µg/kg	Placebo (Pooled)	1.5 µg/kg	3.0 µg/kg	Placebo (Pooled)
XXXXXXXXXX (unit)	X.X-XX.X#	Screen	n	XX	XX	XX			
			Mean	X.XX	X.XX	X.XX			

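### Severity is part of the primary AE outcome, but the SAP tabulates it only as numbers of events, so its tables do not show how many patients had a severe TEAE

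*SAP*

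**What the plan says.** Protocol section 9.2 evaluates safety and tolerability "by number and severity of AEs (including HD vascular access site reactions", alongside other safety measures. SAP section 2.2 repeats the AE component. Relationship to drug is not named in either place.

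On presentation, SAP section 7.3 states: "Tables which tabulate the number of TEAEs by severity and relationship to study treatment will also be included". SAP section 9.2 lists one such table, 14.3.1.3, whose title gives the unit as number of adverse events. Its shell in SAP section 10.3 has, for each term and treatment and for each arm's total, a column headed "Number of Subjects With TEAEs", a column for the number of TEAEs, then grade columns and relationship columns. Two footnote sentences set the counting rule: "If a subject experience the same adverse event (AE) at more than one level of severity during a treatment, each AE is counted separately" and "If a subject experience the same AE at more than one level of drug relationship during a treatment, each AE is counted separately".

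The other AE tables are 14.3.1.1 and its in-text version 12-1 (subjects by system organ class and preferred term, no grade) and 14.3.1.2 (events, no grade). Appendix 16.2.7.1.2 lists severity and relationship by subject.

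**The concern.** A reader of the primary safety result will want to know how many patients on each dose, and on placebo, had a severe event, and how many had a severe event judged related. The planned tables answer a different question: how many events carried each grade. Events within a patient are not independent. In a column of 12, one patient with several events can supply most of a grade cell, or make two columns look alike when very different numbers of patients were affected.

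The footnote matters for the same reason. If a change of grade within one continuing AE produces a new entry, the grade cells also depend on how finely grade changes were recorded.

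**Working it through.** **Column sizes.** Protocol section 14.1 gives 18 patients per cohort at 2:1, so 12 active and 6 placebo. Total: 2 × (12 + 6) = 36, as stated. SAP section 7 pools placebo across cohorts: 6 + 6 = 12. The three columns are therefore 12, 12 and 12, and one patient is 1/12 = 8.3% of a column.

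**What a grade cell says about patients.** Take a row of Table 14.3.1.3 with *s* subjects with TEAEs, *N* events and *g* events at a given grade, each event entered once. Let *m* be the number of patients with at least one event at that grade. Each of the *s* − *m* other subjects needs at least one of the *N* − *g* events at other grades, so for *g* ≥ 1:

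max(1, *s* − (*N* − *g*)) ≤ *m* ≤ min(*g*, *s*)

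In an arm total with enough events at other grades, the lower limit is 1. Assumed counts for illustration:

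| Events at the grade, *g* | Fewest patients | Most patients (if *s* ≥ *g*) |
|---|---|---|
| 6 | 1/12 = 8.3% | 6/12 = 50.0% |
| 7 | 1/12 = 8.3% | 7/12 = 58.3% |

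Two columns could thus both show 6 events at a grade while 50.0% of patients are affected in one and 8.3% in the other. Term-level rows narrow the range only in part: six single-subject rows for six different terms do not show whether the subject is the same.

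**Severe and related.** Grade and relationship are separate margins. Suppose a row holds two events. In case A they are Grade 3 unrelated and Grade 1 possibly related. In case B they are Grade 3 possibly related and Grade 1 unrelated. Both cases print one Grade 1, one Grade 3, one unrelated and one possibly related event. The table cannot separate them.

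**The footnote.** Take one patient whose single AE passes through Grades 1, 2 and 3.

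| Reading | Entries in the grade cells |
|---|---|
| Only separate occurrences are counted separately | 1 |
| Each grade reached is counted | 3, one in each of three cells |
| Patient counted once at worst grade | 1 patient at Grade 3 (8.3%) |

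The SAP does not say which of the first two applies. SAP section 7.3 includes worsening in the definition of a TEAE, but that settles when an event is treatment-emergent, not how often it is counted.

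**Do events cluster within patients?** Protocol section 8.2.2.1 reports 8 TEAEs in the first-in-human study, in 3/16 = 18.75% of active and 1/5 = 20% of placebo subjects (stated as 19% and 20%). Seven events can be placed: two headaches and one puncture-site hemorrhage on active, and four in one person ("Other TEAEs reported included back pain, pruritus, papular rash and skin exfoliation in one placebo subject"). The arm of the eighth is not given. Events per subject:

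- placebo: 4/5 to 5/5 = 0.80 to 1.00
- active: 3/16 to 4/16 = 0.19 to 0.25
- ratio: 0.80/0.25 = 3.2 to 1.00/0.1875 = 5.3

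So one person produced at least 4 of the 8 events, and event rates differed 3.2- to 5.3-fold while the shares of subjects affected were almost equal. This shows clustering of total events only. The grades (5 mild, 3 moderate) are not fully split by arm.

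**The case against.** The case for leaving the plan alone has real substance.

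- **Subject counts are present.** Table 14.3.1.3 prints them beside the event counts for every term and arm. Where a row shows one subject, every graded event in that row is that subject's. Overall clustering is visible. This stands, but the split by grade is still missing.
- **The listings suffice for 36 patients.** Worst grade can be counted by hand from Appendix 16.2.7.1.2, and SAEs have their own listing and narratives. True, but a hand count is not a planned summary. SAP section 1 places additional exploratory analyses outside its scope, and a Grade 3 event need not be serious.
- **Event counting follows the protocol.** Protocol section 8.3.1 describes the endpoint as a number or rate of AEs. This stands: the SAP does not depart from the protocol, and the event table should remain.
- **A patient-level table is also coarse.** It moves by 8.3 points per patient. True, but each patient's weight is then fixed instead of unlimited.

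A reader might also infer two stronger things. One is that relatedness belongs to the primary outcome; sections 9.2 of the protocol and 2.2 of the SAP name only number and severity. The other is that every grade change is counted as a further event; the footnote fits separate occurrences equally well, and Appendix 16.2.7.1.2 shows one severity per AE onset. Only the ambiguity is established.

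**Conclusion.** The gap is real and modest. Severity is a named part of the primary AE outcome and has no planned patient-level table. In general the tables do not show how many of the 12 patients per column had a severe TEAE, or a severe and related one. The footnote leaves open whether one continuing event can occupy several grade cells.

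The size shown, 8.3% to 50.0% of a column behind the same six events, rests on assumed counts and on all 36 planned patients being dosed. It is a limit on what the table can tell, not a forecast.

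It would be wrong to conclude that a treatment comparison or its error rate is compromised: the SAP plans no AE test, and protocol section 14.1 sets the sample size without statistical considerations. It would also be wrong to take the 3.2- to 5.3-fold first-in-human figure as the size of a distortion in severity. It concerns total events against subjects affected, and this SAP, which tabulates both, would reveal such a pattern.

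**What to change.** 1. Add a table of number (%) of patients by worst TEAE grade, and by worst grade among related TEAEs (possibly, probably or likely), for each dose level and pooled placebo. A column for all active patients is optional.
2. Reword the footnote to Table 14.3.1.3 so that a continuing AE whose grade changes is counted once, at its worst grade, while separate occurrences remain separate events.
3. Keep Table 14.3.1.3 as supportive.

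The cost is one extra table from AE data already collected and one changed footnote.
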